3.1 Sample size estimation

After literature search, the literature mainly reported that the scale used for QoL endpoints was AFEQT, and some used the MLHFQ scale. Therefore, the scoring results of the AFEQT scale are summarized as follows.

1. CABANA study

a) The CABANA study compared the effects of medication and catheter ablation on quality of life, and conducted long-term (60 months) AFEQT and MAFSI scales. The population accounted for 946 (42.9%) paroxysmal atrial fibrillation, 1042 (47.3%) persistent atrial fibrillation and 215 (9.8%) long-term persistent atrial fibrillation. The proportion of heart function Class II/III was 776 (35.5%), and the proportion of ejection fraction $\leq 35\%$ was 69 (4.5%).

b) The AFEQT scores for catheter ablation and medical therapy at 3 months were 79.8 (18.6) vs. 76.5 (20.4), and 12 months were 86.4 (16.5) vs. 80.9 (18.5). If the sample calculation is based on the above reference.

i. Based on the AFEQT score at 3 months, the two groups had 550 samples respectively.

Numeric Results for an Unequal-Variance T-Test
 $\delta = \mu_1 - \mu_2$
Hypotheses: H0: $\delta = 0$ vs. H1: $\delta \neq 0$

Target Power	Actual Power	N1	N2	N	μ_1	μ_2	δ	σ_1	σ_2	Alpha
0.8	0.80042	550	550	1100	79.8	76.5	3.3	18.6	20.4	0.05

ii. Based on the AFEQT score at 12 months, the two groups had 161 samples respectively

Numeric Results for an Unequal-Variance T-Test
 $\delta = \mu_1 - \mu_2$
Hypotheses: H0: $\delta = 0$ vs. H1: $\delta \neq 0$

Target Power	Actual Power	N1	N2	N	μ_1	μ_2	δ	σ_1	σ_2	Alpha
0.8	0.80142	161	161	322	86.4	80.9	5.5	16.5	18.5	0.05

2. CABANA sub-study heart failure cohort

a) Paroxysmal atrial fibrillation (AF) accounted for 31.6%, persistent AF accounted for 55.3%, and long-term persistent AF accounted for 13.1%. 79% of patients had a left ventricular ejection fraction (EF) $\geq 50\%$, 11.7% had an EF between 40% and 49%, and 9.3% had an EF $< 40\%$.

b) The scores for catheter ablation and medical therapy at 12 months were 80.6 (19.8) and 75.0

(19.6). If the sample calculation is based on the above reference, 196 patients are needed in each group.

Numeric Results for an Unequal-Variance T-Test

$$\delta = \mu_1 - \mu_2$$

Hypotheses: H0: $\delta = 0$ vs. H1: $\delta \neq 0$

Target Power	Actual Power	N1	N2	N	μ_1	μ_2	δ	σ_1	σ_2	Alpha
0.8	0.80154	196	196	392	80.6	75	5.6	19.8	19.6	0.05

3. CAPLA study

a) The CAPLA study compared the effects of PVI and PVI+PWI ablation strategies on quality of life. The average EF values of the two groups were 51.9 (12.1) vs. 52.6 (12.1), and the proportion of congestive heart failure was 71 (43.3%) vs. 70 (41.7%).

b) Long-term follow-up results showed that the AFEQT scores of PVI and PVI+PWI after catheter ablation were 88.9 (14.8) vs. 88.9 (14.8).

4. KiCS-Af study

a) The KiCS-AF study examined the effects of catheter ablation and drug therapy on heart failure with reduced ejection fraction and preserved ejection fraction, including patients with paroxysmal and persistent atrial fibrillation, with 83.4% of patients having LVEF >35%.

b) The baseline AFEQT in the catheter ablation and drug therapy groups was 71.3 (61.8–82.4) vs. 76.3 (63.0–87.0). The study classified the improvement in AFEQT scores into grades and performed a count analysis. According to the clinical significance of AFEQT improvement >5 points, the change gradient of 5 points, 10 points and 15 points was graded and the difference in the rates between the two groups was compared. There was no mean result.

5. RAFT-AF study

a) The RAFT-AF study evaluated the effects of catheter ablation and medication in patients with atrial fibrillation and heart failure. The proportion of patients with ejection fraction > 45% was 41% .

b) The AFEQT evaluation score was the difference between the baseline and follow-up nodes. The results of rate control versus catheter ablation rhythm control were 16.1 ± 1.6 versus 23.4 ± 1.5 .

Based on this sample size, only 3 cases in each group were required.

$$\delta = \mu_1 - \mu_2$$

Hypotheses: H0: $\delta = 0$ vs. H1: $\delta \neq 0$

Target Power	Actual Power	N1	N2	N	μ_1	μ_2	δ	σ_1	σ_2	Alpha
0.8	0.98614	3	3	6	16.1	23.4	-7.3	1.6	1.5	0.05

6. RCT STALL HFpEF

a) This is the first RCT on HFpEF, but the sample size is only 31 patients.

b) According to the AFEQT score results at six months, the results of the catheter ablation group and the drug therapy group were 75.2 ± 19.9 and 57.3 ± 23.5 , respectively. The sample size was calculated to be 25 cases in each group.

Numeric Results for an Unequal-Variance T-Test

$$\delta = \mu_1 - \mu_2$$

Hypotheses: H0: $\delta = 0$ vs. H1: $\delta \neq 0$

Target Power	Actual Power	N1	N2	N	μ_1	μ_2	δ	σ_1	σ_2	Alpha
0.8	0.81226	25	25	50	75.2	57.3	17.9	19.9	23.5	0.05

In view of the heterogeneity of the above study population and results, it is recommended that:

1、 The AFEQT value of the endpoint of the pulse catheter ablation group be selected from the

CABANA heart failure cohort at 12 months, which is 80.6 (19.8). Referring to the KiCS-AF cohort study, which divided the AFEQT improvement value into three levels of 5, 10 and 15, we set the AFEQT value of the drug treatment group to 75.6/70.6/65.6.

2、 Set the AFEQT of the drug group to 75.6, $\alpha=0.05$, $\beta=0.2$, and 248 patients are required in each group.

Numeric Results for an Unequal-Variance T-Test

$$\delta = \mu_1 - \mu_2$$

Hypotheses: $H_0: \delta = 0$ vs. $H_1: \delta \neq 0$

Target Power	Actual Power	N1	N2	N	μ_1	μ_2	δ	σ_1	σ_2	Alpha
0.8	0.80138	248	248	496	80.6	75.6	5	19.8	19.8	0.05

3、 Set the AFEQT of the drug group to 70.6, $\alpha=0.05$, $\beta=0.2$, and 63 cases are needed in each group. Considering a dropout rate of 20%, 79 cases are needed in each group.

Numeric Results for an Unequal-Variance T-Test

$$\delta = \mu_1 - \mu_2$$

Hypotheses: $H_0: \delta = 0$ vs. $H_1: \delta \neq 0$

Target Power	Actual Power	N1	N2	N	μ_1	μ_2	δ	σ_1	σ_2	Alpha
0.8	0.80306	63	63	126	80.6	70.6	10	19.8	19.8	0.05

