The following information should be collected/completed at the $6m \pm 15d$ follow-up after surgery:

- ◆ Vital signs
- ◆ Standard electrocardiogram
- ◆ Holter
- ◆ AFEQT quality of life score for patients with atrial fibrillation
- ◆ Cardiac ultrasound
- ◆ Medication status
- ◆ Adverse events & serious adverse events

(7) V8 12 months post-surgery

The following information should be collected/completed at the $12m \pm 15d$ follow-up after surgery:

- ◆ Vital signs
- ◆ Laboratory tests
- ◆ Standard electrocardiogram
- ◆ Holter
- ◆ AFEQT quality of life score for patients with atrial fibrillation
- ◆ Cardiac ultrasound

- ◆ Medication status
- ◆ Adverse events & serious adverse events

Note: Medication status: Record the medication status during the study period (from signing the informed consent to the end of follow-up). Routine solution preparation (normal saline, glucose solution), intraoperative anesthetics, and intraoperative anticoagulants do not need to be recorded. Drugs used for corrective treatment of adverse events also need to be recorded.

Adverse events: Record clinically significant adverse events of the subjects from signing the informed consent to the end of follow-up. Events in which the health status of the subjects does not deteriorate seriously due to planned hospitalization for existing diseases or follow-up required by the protocol are not recorded as serious adverse events.

5. End point

5.1. Primary endpoint:

Change in quality of life at 12 months as measured by the Atrial Fibrillation Quality of Life Survey (AFEQT). Improvement in quality of life from baseline to 12 months after pulsed field ablation procedure or AAD as measured by the Atrial Fibrillation Quality of Life Survey (AFEQT), with values ranging from 20 - 140 (higher scores mean worse outcomes).

5.2 Secondary endpoint:

- (1) The rate of atrial fibrillation-free recurrence during clinical follow-up within 12 months after surgery, that is, the success rate of pulsed field therapy for AF (including atrial tachycardia (AT) lasting more than 30 seconds, atrial flutter (AFL), and AF endpoint events);
- (2) Complications and adverse events during the pulsed field ablation surgery and during the postoperative follow-up, including readmission, cardiovascular events, cardiovascular death, all-cause death, and also including serious adverse events related to the surgery.
- (3) Rehospitalization due to heart failure or recurrence of atrial fibrillation 3 months after surgery;

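### The 80% power is calculated for 12-month AFEQT scores, but the primary endpoint is change from baseline, so the power is not established for that endpoint

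*Protocol*

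**What the plan says.** Section 5.1 (and the summary table) sets the primary endpoint as "Improvement in quality of life from baseline to 12 months after pulsed field ablation procedure or AAD", measured by AFEQT.

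Section 3.1 sizes the study on a different quantity. Its source is the heart failure cohort of CABANA: "The scores for catheter ablation and medical therapy at 12 months were 80.6 (19.8) and 75.0" (SD 19.6 for the latter). The ablation value is taken from the "CABANA heart failure cohort at 12 months, which is 80.6 (19.8", the bracketed figure being the SD. For the comparator, the protocol refers to the KiCS-AF study, "which divided the AFEQT improvement value into three levels of 5, 10 and 15", and on that basis "we set the AFEQT value of the drug treatment group to 75.6/70.6/65.6". The chosen scenario reads "Set the AFEQT of the drug group to 70.6, $\alpha=0.05$, $\beta=0.2$, and 63 cases are needed in each group". A 20% dropout allowance brings this to 79 per group, 158 in total. The test behind the figure is a two-sided unequal-variance t-test with SD 19.8 in both groups.

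The same section reports for KiCS-AF: "The baseline AFEQT in the catheter ablation and drug therapy groups was 71.3 (61.8–82.4) vs. 76.3 (63.0–87.0".

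The only change-score result cited is RAFT-AF (16.1 ± 1.6 against 23.4 ± 1.5). It produced 3 per group and was not used for the final number. The data analysis part of section 9 names no method for AFEQT; its one t-test line concerns molecular data.

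**The concern.** A change score and a final score have different variances. With equal SDs at both times, change is more variable than the final score when the correlation is below 0.5 and less variable when it is above. A power figure for one therefore says nothing definite about the other until the correlation, or the SD of change, is stated. The protocol states neither.

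The effect size has a parallel problem. Steps of 5, 10 and 15 points that grade a patient's own improvement have been subtracted from a 12-month group mean. Under randomisation the expected between-group difference is the same for final score and for change, and the borrowing would do little harm. This study is a cohort and describes no randomisation, so the two differences agree only if the groups start level. What is at stake is whether the sample-size statement supports the primary comparison the protocol announces.

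**Working it through.** **Inputs.** From section 3.1: means 80.6 and 70.6 (difference 10), SD 19.8 in each group, two-sided alpha 0.05, 63 per group, 20% dropout. Not in the protocol, so assumed: the correlation ρ between baseline and 12-month AFEQT (range 0.2 to 0.7) and the baseline SD (19.8 unless stated).

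**Step 1: reproduce the plan's figure.** The standard error of the difference is 19.8 × √(2/63) = 3.53, so the noncentrality is 10/3.53 = 2.83. Power from the noncentral t distribution with 124 df is 0.80306, exactly as printed, and 63 is the smallest n reaching 80%. Dropout: 63/0.8 = 78.75, rounded up to 79. Nothing is miscalculated for final scores.

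**Step 2: the same calculation for change.** With equal SDs, SD of change = 19.8 × √(2(1 − ρ)). The difference in change is taken as 10.

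**Step 3: the same calculation with baseline as covariate.** Residual SD = 19.8 × √(1 − ρ²). The baseline-adjusted difference is taken as 10, with balanced baselines.

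| ρ (assumed) | SD of change | Power, change, 63/group | n/group for 80%, change | Residual SD, adjusted | Power, adjusted, 63/group |
|---|---|---|---|---|---|
| 0.2 | 25.05 | 60% | 100 | 19.40 | 82% |
| 0.3 | 23.43 | 66% | 88 | 18.89 | 84% |
| 0.4 | 21.69 | 73% | 75 | 18.15 | 87% |
| 0.5 | 19.80 | 80% | 63 | 17.15 | 90% |
| 0.6 | 17.71 | 88% | 51 | 15.84 | 94% |
| 0.7 | 15.34 | 95% | 38 | 14.14 | 98% |

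**Step 4: unequal SDs.** In general, SD of change = √(19.8² + s² − 2ρ × 19.8 × s), where s is the baseline SD. This equals 19.8 when ρ = s/(2 × 19.8). The break-even is 0.5 for s = 19.8, 0.38 for s = 15 and 0.56 for s = 22. With s = 15, power for change is 76% at ρ = 0.3 and 88% at ρ = 0.5; with s = 22 it is 61% and 76%.

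**Step 5: what 10 points means when baselines differ.** The KiCS-AF baselines differ by 76.3 − 71.3 = 5 points, ablation lower. They are illustrative only, since they appear to be medians with ranges. With that gap:

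- a 10-point gap in 12-month scores is a 10 + 5 = 15-point gap in change;
- a 10-point gap in change is a 10 − 5 = 5-point gap in 12-month scores. For a 5-point gap the protocol's own calculation asks for 248 per group; power at 63 is 29%.

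The two readings of 10 points thus lead to very different studies.

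**The case against.** Four points on the other side deserve weight.

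- **No number is wrong.** This stands. The 63, the 0.80306 and the 79 all reproduce. The fault is that the quantity sized is not the quantity defined as the endpoint.
- **The protocol declares no AFEQT analysis.** This also stands. A reader might infer that a t-test on raw change is planned, and that the 80% therefore fails for the planned test. The protocol does not say so, and the choice between raw change and a baseline-adjusted model could properly sit in an SAP that is not shown. It does not remove the point: the endpoint and the power statement are both in the protocol and describe different quantities.
- **No loss of power is demonstrated.** Correct. The figures below 80% need a low assumed correlation, and the figures above it are just as much assumed. If the KiCS-AF brackets are read as interquartile ranges (an assumption; width/1.349), the baseline SDs are about 20.6/1.349 = 15.3 and 24.0/1.349 = 17.8. The break-even correlation then falls to about 0.39 and 0.45, and the low-end powers in the table are somewhat pessimistic. The KiCS-AF gap can also help: a 15-point difference in change gives at least 91% power for correlations of 0.2 or more.
- **Baseline adjustment does not guarantee 80%.** Correct. If the 10 points stay a gap in 12-month scores and the drug group happens to start 5 points lower, the adjusted difference is 10 − 5ρ. Power at 63 per group is then roughly 68% to 73% for ρ from 0.2 to 0.5. The range of 82% to 98% needs the 10 points to be the adjusted difference. On that definition a 5-point baseline gap costs little through variance inflation (about 81% to 97%).

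**Conclusion.** The mismatch is real and lies in the protocol's own text: the endpoint is change, the sizing is on 12-month scores, and nothing connects them. The 80% is correct for final scores and unestablished for change. For a 10-point difference in change and a baseline SD of 19.8, power at 63 per group runs from about 60% (ρ = 0.2) to 95% (ρ = 0.7), crossing 80% at ρ = 0.5, or at a lower ρ if the baseline SD is smaller. The assumed effect is also ambiguous, because improvement grades are used as a gap between final means in a study where baselines may differ.

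A reader might conclude that the study is underpowered or that N must rise. The protocol supports neither, because it gives no correlation and no usable SD of change. The finding is that the power claim lacks its basis, which should be corrected because it concerns the primary endpoint.

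**What to change.** Make these changes in sections 3.1, 5.1 and 9 together:

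1. Name the primary comparison as a linear model of 12-month AFEQT (or of change) on treatment group, with baseline AFEQT as covariate. Both forms give the same group estimate.
2. Define the 10 points as the baseline-adjusted difference between groups, and say why that size is assumed.
3. Restate the power for that model with the assumed SD and correlation, their source, and a range. If raw change is preferred instead, state the SD of change and recompute N from it.
4. In the same edit, reconcile the scale. Section 5.1 gives AFEQT a range of 20 to 140 with higher scores worse, while section 3.1 treats a higher score as the benefit. The SD of 19.8 and the 10 points can be carried to the endpoint only once both sections use one scale.

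Baseline AFEQT is already collected at screening, so the adjusted analysis needs no new data. With SD 19.8, near-balanced baselines and a 10-point adjusted difference, 63 evaluable per group (158 enrolled) can stay. That is conditional on those assumptions, and adjusting for baseline AFEQT does not remove other confounding between the groups.

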3.2 Subject screening

Whether the selected patients meet the inclusion criteria requires the following assessments:

- (1) General information: age, gender, place of origin, contact information, etc.
- (2) Physical examination: height, weight; heart rate, blood pressure, etc.
- (3) Past medical history: hypertension, diabetes, coronary heart disease, cardiomyopathy, COPD, stroke, etc.; previous surgical history, including pacemaker implantation, thyroid disease history, etc.; previous medication history;
- (4) Electrocardiogram (including Holter);
- (5) Transthoracic echocardiogram (LVEF, LVEDD, LAD, e/e', etc.);
- (6) Transesophageal echocardiogram, MRI or CT examination of the left atrium and pulmonary veins;
- (7) Laboratory tests: routine blood tests, routine urine tests, routine stool tests, liver function tests, kidney function tests, electrolytes, blood sugar, blood lipids, myocardial markers, coagulation function tests, BNP or NT-proBNP, thyroid function tests, etc.
- (8) Informed consent was signed for the subjects who met the above requirements and agreed to participate in the study.

In this study, no examination items were included beyond those required for routine diagnosis and treatment.

3.3 Inclusion Criteria

- (1) Age 18-80 years;
- (2) Patients with persistent atrial fibrillation;

(3) According to the 2021 European Society of Cardiology (ESC) guidelines for heart failure, heart failure with preserved ejection fraction (HFpEF) is defined as patients with preserved or slightly reduced left ventricular ejection fraction (LVEF) but with diastolic dysfunction. The diagnostic criteria for HFpEF include: symptoms and signs of heart failure; LVEF $\geq 50\%$; and objective evidence of cardiac structural and functional abnormalities consistent with left ventricular diastolic dysfunction or increased left ventricular filling pressure. These can be verified by imaging examinations such as echocardiography and biomarkers such as B-type natriuretic peptide or NT-proBNP. The thresholds for B-type natriuretic peptide or NT-proBNP are: BNP ≥ 35 pg/mL or NT-proBNP ≥ 125 pg/mL for patients with sinus rhythm; BNP ≥ 105 pg/mL or NT-proBNP ≥ 365 pg/mL for patients with atrial fibrillation.

(4) Agree to participate in this study and sign the informed consent form. Have clinical compliance to complete the postoperative follow-up required by the protocol.

3.4 Exclusion criteria

- (1) Patients with persistent atrial fibrillation lasting for more than 3 years,
- (2) Patients who had used class I or class III antiarrhythmic drugs, but the use of the above drugs for less than 7 days to convert atrial fibrillation was allowed;
- (3) Previous left atrial ablation or surgery (including left atrial appendage occlusion);
- (4) Left atrial diameter > 50 mm;
- (5) Previous pulmonary vein stenting;
- (6) Previous pulmonary vein stenosis;
- (7) Presence of any heart valve prosthesis;
- (8) Any cardiac surgery, myocardial infarction, percutaneous coronary intervention (PCI)/percutaneous transluminal coronary angioplasty (PTCA) or coronary artery stenting within three months before signing the informed consent;
- (9) Unstable angina or severe coronary artery stenosis;
- (10) Primary pulmonary hypertension;
- (11) Rheumatic heart disease;
- (12) Thrombocytosis, thrombocytopenia;
- (13) Any disease that prohibits long-term anticoagulation;
- (14) Active systemic infection;
- (15) Atrial fibrillation caused by reversible causes, such as hyperthyroidism;
- (16) Women known to be pregnant or breastfeeding;
- (17) Life expectancy of less than one year;
- (18) Patients with intracardiac thrombus;
- (19) Patients with known drug or alcohol addiction;

- (20) Patients who are unwilling or unable to fully comply with the study protocol and complete follow-up;
- (21) Patients with malignant tumors;
- (22) Participating in other clinical trials that may interfere with the results

3.5 Exit Criteria

The criteria for subject withdrawal include, but are not limited to:

- (1) The subject requests withdrawal;
- (2) The researcher determines that the subject is not suitable to continue participating in the study;

The subject has the right to withdraw at any stage of the clinical trial without any financial responsibility, and has the right to withdraw at any stage of the trial without being discriminated against or retaliated against, and their medical treatment and rights are not affected. The withdrawal of the subject from the clinical trial should be recorded in the relevant research materials.

3.6 Elimination criteria

The criteria for subject exclusion include, but are not limited to: misdiagnosis; no examination or observation records;

The reasons for exclusion should be stated, and no statistical analysis of efficacy will be performed; if the patient receives treatment and has at least one safety record, he or she may participate in the safety analysis depending on the situation.

3.7 Criteria and procedures for stopping the trial/trial treatment

The criteria for stopping the study/trial treatment include, but are not limited to:

- (1) The subject withdraws from the trial;
- (2) Unexpected serious adverse events of the device occur, causing serious danger to the subjects participating in the study;
- (3) The medical device regulatory authority or ethics committee requires the trial to be stopped;
- (4) Other circumstances that require the trial/trial treatment to be stopped;

Procedures for Discontinuation of Study/Study Treatment:

- (1) Subjects withdraw from the study: Regardless of the reason, the records of cases withdrawing from the study should be retained, and the last evaluation and examination results should be carried forward as the final results, and the full data set analysis should be conducted on their efficacy and safety. The study conclusions and reasons for the withdrawal of all cases should be recorded;

(2) Ethics Committee requires the study to be stopped: For ethical and scientific reasons, the ethics committee requires the study to be stopped. After the researcher learns of the situation, the researcher should stop the study in a timely manner and keep the communication records or written documents of the study cessation;

(3) Regulatory agency requires the study to be stopped: If the medical device supervision and management department requires the study to be stopped, the person in charge of the study should notify each research unit in writing in a timely manner after learning of the situation;

(4) Other situations where the study/research treatment must be stopped: The situation where the subject stops the study/research treatment due to illness or other reasons should be recorded in detail; the cessation of the entire study should be reported to each research unit in writing in a timely manner; other situations where the study/treatment must be stopped should also be recorded in detail.

4. Study plan

4.1 Treatment of patients in the drug group:

Patients who enter the drug group after screening can receive electrical cardioversion or drug cardioversion for drug treatment. If the patient undergoes electrical cardioversion, preoperative examinations must be completed before surgery to exclude surgical contraindications.

The blank period starts from the day 0 when the patient receives Class I or Class III antiarrhythmic drugs, and the blank period of the drug group is from Day 0 to the next 90 days. During the blank period, patients can undergo electrical cardioversion to recover to sinus rhythm (if patients have recurrent atrial fibrillation during the blank period, they can choose to undergo electrical cardioversion again without the limit of countless times). Titration and adjustment of antiarrhythmic drugs are allowed during the blank period. In principle, no drug adjustments will be made after the blank period. Increasing the dose of the original Class I or Class III drugs or replacing antiarrhythmic drugs due to intolerance or drug side effects is considered the end point. Adding Class II or Class IV antiarrhythmic drugs for other reasons is allowed.

4.2 Treatment of patients in the surgical group::

4.2.1 Preoperative preparation:

(1) Class II and IV antiarrhythmic drugs, diuretics, digitalis drugs, etc. are allowed before surgery. The purpose is to control ventricular rate and improve heart failure treatment. The researcher can decide whether to continue taking the above-mentioned drugs;

(2) Anticoagulants, including warfarin and new oral anticoagulants, should not be discontinued before surgery. For warfarin, INR should be routinely tested before surgery;

(3) Complete preoperative examinations to exclude surgical contraindications (such as left atrial thrombus, abnormal coagulation function, severe thrombocytopenia, liver dysfunction, acute renal dysfunction, acute heart failure, etc.).

4.2.2 Intraoperative operation:

(1) General anesthesia;

(2) Heparin anticoagulation and maintaining ACT at 250-350 seconds;

(3) Single atrial septal puncture via femoral vein;

(4) Conventional PulseSelect PFA ring catheter preparation: flush the guidewire cavity, then insert the guidewire into the catheter through the guidewire Luer interface, retract the ring electrode into the introducer, slowly push the catheter slide control button forward to make the ring electrode linear, and at the same time push the introducer to retract the ring electrode. PulseSelect PFA ring catheter is inserted into the sheath.

(5) Pulmonary vein orifice-vestibular step ablation: advance the catheter along the adjustable curved sheath until the guidewire enters the left atrium. Before fully deploying the ring tip, ensure that the guidewire is advanced into the orifice of one of the left pulmonary veins for at least 5 cm. Continue to advance the catheter along the guidewire until the fourth electrode on the ring spiral begins to leave the sheath, and the catheter tip forms a ring in the LA. It is recommended to perform at least 8 ablations for each pulmonary vein, at least 4 ablations for the ostium and at least 4 ablations for the vestibule, with 4 pulse sequences in each ablation.

(6) Use the PulseSelect PFA catheter to determine bidirectional block. Use the PulseSelect catheter for pacing bidirectional block determination according to the standard electrophysiological procedure.

(7) Cardioversion after PVI ablation for persistent atrial fibrillation;

(8) Perform matrix mapping under sinus rhythm after cardioversion. If the voltage of the posterior wall of the left atrium is low, pulse ablation can be performed. If there is a trigger focus in the superior vena cava, pulse field ablation of the superior vena cava can be performed;

(9) Record the intraoperative medication situation;

(10) Record the rhythm changes during the operation, whether cardioversion was performed, and the rhythm changes after cardioversion;

(11) Record the intraoperative and postoperative complications and adverse event monitoring, including surgery-related death, atrial esophageal fistula, acute coronary syndrome, vascular events at the puncture site (requiring surgical intervention), severe hematoma, pericardial tamponade or pericardial effusion requiring puncture drainage, thromboembolic events, stroke/transient ischemic attack, pulmonary edema, pulmonary vein stenosis, etc.

